OBJECTIVES	
The primary objective of the BLUEPRINT Study is to comprehensively define the respiratory phenotype and endotypes using observations from the first 7 days after birth in preterm infants born between 22+0 and 31+6 weeks' gestation.
 
The secondary objectives of this study are:
 
 1. To compare the respiratory endotypes associated with different respiratory outcomes using observational data at 72 hours after birth in preterm infants born between 22+0 and 31+6 weeks' gestation. 2. To develop the first functional classification of preterm respiratory disease using a combination of clinical, lung imaging and molecular biomarkers. 3. Determine how specific early preterm endotypes relate to a diagnosis of BPD to develop a predictive modelling tool for the early diagnosis of BPD that can be used in everyday clinical practice. 4. Determine how specific early preterm endotypes relate to outcomes of the primary NICU admission, including duration of invasive mechanical ventilation and supplementary oxygen support, mortality, need for supplementary oxygen at discharge home. 5. To characterise the respiratory health of preterm infants in the first 2 years (corrected) after birth. 6. To characterise overall childhood health of preterm infants in the first 2 years (corrected) after birth. 7. To determine the relationship between initial respiratory endotype, BPD status and early childhood respiratory health at 1 and 2 years of corrected age. 8. To determine the performance of early life endotypes against a 36-week diagnosis of BPD in predicting respiratory outcomes at 1 and 2 years of corrected age. 9. To determine the relationship between LUS-derived measures of respiratory status at 14 and 28 days after birth and BPD status. 10. To determine the relationship between EIT-derived measures of respiratory status at 14 and 28 days after birth and BPD status.

Study Name: The BLUEPRINT Study

Protocol Number: 107608

Version & date: Version 1.2, dated 9 July 2024

	
 11. To use plasma proteomics to identify proteins whose expression is altered in the first 7 days of life in infants who later are diagnosed with BPD. 12. To use plasma proteomics to identify expression pathways associated with specific preterm respiratory endotypes in samples obtained at 72 hours and 7 days post-birth. 13. To determine the impact of clinical interventions on the development of the respiratory phenotype.
OUTCOMES AND OUTCOME MEASURES	
The primary outcome is identification of functional endotypes defined from clinical, plasma protein and lung imaging measures using cross-sectional and longitudinal latent class analysis.
 
The secondary outcomes include the functional endotype at 72 hours, the relationship between early life phenotypes, proteomic and lung imaging and later BPD status and respiratory health at 1 and 2 years of corrected age, and the development of prediction models for BPD using the early life respiratory endotypes.

EXPOSURES	
Eligible and enrolled infants will have clinical data relating to their antenatal, maternal and postnatal respiratory and neonatal intensive care course collected at pre-defined time points between birth and NICU discharge.
 
In addition, a maximum of 0.5 ml of blood will be collected at 72 hours and 7 days, and a brief LUS and EIT image of the lung performed at 48 and 72 hours, 7, 14 and 28 days, and then at 36 weeks' postmenstrual age (BPD diagnosis). Lung imaging and assessment of respiratory health using a standardised questionnaire will be repeated at 1 and 2 years corrected age in preterm survivors.

POTENTIAL CONFOUNDING FACTORS	
Maternal and antenatal factors and management, clinical decisions regarding respiratory support (site and clinician differences in guidelines and management), preterm non-respiratory complications (such as infection, neurological disease, necrotising enterocolitis, jaundice).

STUDY POPULATION	
Infants born between 22+0 and 31+6 weeks' gestation admitted to a participating centre from whom prospective parental informed consent can be obtained will be considered eligible. If parental consent cannot be obtained or if lung imaging or blood sampling would compromise clinical care or well-being, the infant will be considered ineligible for participation in this study.
 
A sample size of 550 infants will allow for prediction models of BPD using up to 12 variables from the respiratory phenotype data collected in the first 7 days after birth with a C-index of 0.75 (assuming 5% lost to follow up). This sample size will have sufficient power to address the endotyping and respiratory health

	objectives of the study at 1- and 2-years corrected age, with account for anticipated loss to follow up rates.
DESCRIPTION OF SITES ENROLLING PARTICIPANTS	All Level 6 NICUs in Melbourne, Victoria (Australia) will be invited to participate (5 sites maximum).
RECRUITMENT PERIOD	Approximately 5 years after first infant enrolled.
FOLLOW-UP PERIOD	2 years, assessments at 1- and 2-years (corrected).
PARTICIPANT DURATION	2 years, corrected age from birth.

GLOSSARY OF ABBREVIATIONS

ABBREVIATION	TERM
AE	Adverse Event
ANOVA	Analysis of Variance
ANZNN	Australian and New Zealand Neonatal Network: a collaborative network which monitors and reports on the care of high-risk newborns in all Australian and New Zealand neonatal intensive care units.
BPD	Bronchopulmonary dysplasia: a form of chronic lung disease that affects preterm infants
CLD	Chronic Lung Disease
CCe	Coordinating Centre
CRF / eCRF	Case Report Form / electronic Case Report Form
CXR	Chest Radiography
DCCe	Data Coordinating Centre
DMS	Data Management System
DSMC	Data Safety Monitoring Committee
EDTA	Ethylenediaminetetraacetic acid: used as an anticoagulant in blood tubes
EIT	Electrical Impedance Tomography
EMR	Electronic Medical Record
ETT	Endotracheal Tube
FiO₂	Fraction of Inspired Oxygen
GA	Gestational age
GCP	Good Clinical Practice
HR	Heart Rate
HREC	Human Research Ethics Committee
IVH	Intraventricular Haemorrhage
LCA	Latent Class Analysis
LUS	Lung Ultrasound
LUSS	Lung Ultrasound Score

Study Name: The BLUEPRINT Study

Protocol Number: 107608

Version & date: Version 1.2, dated 9 July 2024

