2.2 Definitions

The following definitions are applicable to this study:

Phenotype = any observable characteristic or trait of a disease, such as the clinical presentation of an individual. There is no implication of a mechanism.

Endotype = an endotype is defined by a distinct function or pathobiological mechanisms that manifest in or are exhibited by a phenotype or cluster of phenotypes.

An early life preterm respiratory-specific endotype may present with phenotypic clusters of disease. Preterm respiratory-specific endotypes can be specific to a particular time-point and can also be defined longitudinally over the first 2 years after birth (corrected for gestation).

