3.2 Outcomes

Table 3a defines the outcomes measures in relation to objectives and confounders.

Table 3a Listing objectives, exposure, outcomes and outcome measures, and confounders

PRIMARY OBJECTIVE
To comprehensively define the respiratory phenotype in the first 7 days after birth of preterm infants born between 22+0 and 31+6 weeks' gestation.

Exposure:
 
Day 7 after birth.

Outcome & outcome measure:
 
Functional endotypes defined from clinical, plasma protein and lung imaging measures using latent class analysis followed by external validation via group-based trajectory modelling.

Confounding factors:
 
Maternal and antenatal factors and management, clinical decisions regarding respiratory support (site and clinician differences in guidelines and management), preterm non-respiratory complications (such as infection, neurological disease, necrotising enterocolitis).

SECONDARY OBJECTIVES
To compare the respiratory endotypes associated with different respiratory outcomes using observational data at 72 hours after birth in preterm infants born between 22+0 and 31+6 weeks' gestation.

Outcome & outcome measure
 
Functional endotypes defined from clinical, plasma protein and lung imaging measures using latent class analysis (LCA) followed by external validation via group-based trajectory modelling.

To develop the first functional classification of preterm respiratory disease using a combination of clinical, lung imaging and molecular biomarkers.

Outcome & outcome measure
 
Temporally specific respiratory phenotypes derived from longitudinal latent class analysis of clinical, lung imaging and molecular biomarker data from all time points of the study.

To determine how specific early preterm phenotypes relate to a diagnosis of BPD and use this delineation to develop a predictive modelling tool for the early diagnosis of BPD.

Outcome & outcome measure

BPD status at 36 weeks' corrected PMA using Walsh Definition and Jensen Grade of Severity and functional endotypes determined above.
SECONDARY OBJECTIVES cont.
To determine how specific early preterm endotypes relate to outcomes of the primary NICU admission, including duration of invasive mechanical ventilation and supplementary oxygen support, mortality, need for supplementary oxygen at discharge home.
Outcome & outcome measure

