4.3.2 Inclusion Criteria

Each infant must meet all inclusion criteria to be eligible for enrolment on this study:

1. Born between 22+0 and 31+6 weeks' gestation.
2. Birth admission in a participating perinatal Victorian NICU.
3. The infant has a parent/legal representative capable of understanding the informed consent document and providing consent on the infant's behalf AND consent is obtained antenatally or within 72 hours from birth.

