9.2 Data confidentiality

Infant confidentiality is strictly held in trust by the PI, participating investigators, research staff, and the sponsoring institution and their agents. This confidentiality is extended to cover testing of biological samples and genetic tests in addition to the clinical information relating to participating participants.

To preserve confidentiality and reduce the risk of identification during collection, analysis and storage of data and information, the following will be undertaken:

(1) The number of sensitive/confidential variables collected for each infant has been minimised. The data collected will be limited to that required to address the primary and secondary objectives.

(2) Infant identifiers will be stored separately to the data collected; documents with identifiers will be stored separately to infant data. Infant data and samples will be identified through use of a unique participant study number/code assigned to the study infant (“re-identifiable”). Plasma samples will be bar-coded with a unique barcode that will be linked to the unique infant study number/code via REDCap. The Site PI is responsible for the storage of a master-file of names and other identifiable data with the infant ID; access to this document will be restricted to the site study team and authorised persons as listed previously. The master file should be stored securely, and separately, from study data in locked/password-protected databases with passwords kept separately. Due to the study population and study aims, GA at birth, sex and age will need to be documented in the study CRFs (GA and sex are major determinants of respiratory status after preterm birth, and age is needed to coordinate scheduled assessments).

(3) Separation of the roles responsible for management of identifiers and those responsible for analysing content. The data will be analysed by the statistician, who will be provided with anonymised data identified only by the unique infant study ID.

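### The primary outcome has no result that counts as 'no distinct endotypes', and a standard latent class analysis can meet it by slicing a smooth gestation or severity gradient into classes

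*Protocol*

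**What the plan says.** The synopsis (Outcomes and outcome measures) makes the primary outcome "identification of functional endotypes defined from clinical, plasma protein and lung imaging measures using cross-sectional and longitudinal latent class analysis". Section 3.2, Table 3a, repeats it for the primary objective and adds a second step: "using latent class analysis followed by external validation via group-based trajectory modelling".

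Section 2.2 sets a higher bar than a statistical class: "an endotype is defined by a distinct function or pathobiological mechanisms". Section 4.3.2 admits infants "Born between 22+0 and 31+6 weeks' gestation", a continuous range of almost ten weeks. Section 9.2 states that "GA and sex are major determinants of respiratory status after preterm birth", and section 11.1 likewise lists gestational age and sex among factors with a strong influence on neonatal outcome.

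The confounders for the primary objective in Table 3a begin "Maternal and antenatal factors and management, clinical decisions regarding respiratory support" and go on to non-respiratory complications. Neither gestational age nor sex is named there or in the matching synopsis entry. Neither place says what would be concluded if one class, or a continuum, described the data best.

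**The concern.** Basic latent class and latent profile models assume that indicators are independent within a class. A continuous driver shared by the indicators breaks that assumption in a one-class model, and adding classes is the only way such a model can absorb the resulting correlation. The fitted classes may then be slices of gestation or of severity, not groups with distinct mechanisms. An outcome worded as identification, with no null result, would count both as success.

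The consequence extends beyond the primary outcome. Secondary objectives 1, 3, 4, 7, 8 and 12 in section 3.1.2 reuse the endotypes. Classes that mostly encode gestation could appear to predict BPD and 1- and 2-year health because gestation does.

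**Working it through.** **The protocol's own figure.** The only computed sample size (section 11.1) is for the BPD prediction model. With C-index 0.75 and prevalence 0.69, simulation gives a Cox-Snell R² of 0.1628. The shrinkage criterion is n = P / [(S − 1) ln(1 − R²/S)] with S = 0.9. The denominator is −0.1 × ln(1 − 0.1809) = 0.01995, so n = 502, 552 and 602 for P = 10, 11 and 12, against the stated 500, 550 and 600. The figure reproduces but does not concern the primary outcome. For endotyping, the synopsis asserts adequate power without a calculation.

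**Why classes appear.** Let each of 10 indicators correlate ρ with gestation and share nothing else. Any two indicators then correlate r = ρ². Treating the data as normal, the average deviance lost by assuming independence at n = 550 is −550 × ln[(1 − r)⁹(1 + 9r)]. With equal variances, a second class costs 10 means plus 1 proportion, so the BIC penalty is 11 × ln 550 = 69.

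| ρ | r | deviance to be gained | BIC penalty |
|---|---|---|---|
| 0.2 | 0.04 | 33 | 69 |
| 0.3 | 0.09 | 140 | 69 |
| 0.4 | 0.16 | 372 | 69 |
| 0.5 | 0.25 | 776 | 69 |

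Two classes recover only part of the gain, and chance fit is ignored. The table still shows why the switch falls between 0.2 and 0.3.

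**Simulation, no true classes.** Inputs: n = 550 (synopsis and section 1.3); gestation uniform over the eligible range; indicators linear in gestation plus independent normal noise; lowest BIC, with one class allowed; 60 datasets per setting. The values of ρ are assumed. Share choosing two or more classes:

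| Model | ρ = 0 | 0.2 | 0.3 | 0.4 | 0.5 |
|---|---|---|---|---|---|
| Latent profile, 6 indicators | 0% | 3% | 85% | 100% | 100% |
| Latent profile, 10 indicators | 0% | 0% | 80% | 100% | 100% |
| Latent profile, 12 indicators | 0% | 8% | 100% | 100% | 100% |
| Binary latent class, 6 | 0% | 0% | 12% | 100% | 100% |
| Binary latent class, 12 | 0% | 0% | 90% | 100% | 100% |
| Trajectory model, 1 marker at 4 times | 0% | 2% | 83% | 100% | not completed |

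A shorter run with 12 indicators at 0.2 gave 13% (4 of 30). Replacing uniform gestation by the 37% below 28 weeks in section 11.1 (10 indicators, shape within strata assumed) gave 3%, 100%, 100% and 100% at 0.2 to 0.5. Across the 10-indicator runs at 0.3 to 0.5, the chosen classes explained 35% to 66% of gestation variance. An unmeasured normal severity factor, with no gestation effect, gave 0%, 75%, 100% and 100% at loadings 0.2 to 0.5.

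**Does a continuous comparison help?** In two sets of gradient datasets, a one-factor model beat every class model by BIC in 67% to 72% at 0.3, 70% to 82% at 0.4, and 100% at 0.5. When two real classes existed, it won in 0% to 15% at 0.3 and 0% at 0.4; at 0.5, checked in one set only, it won in 0%. A factor-mixture model was not simulated.

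**Does conditioning on gestation help?** Removing linear gestation first gave two or more classes in 0% of datasets at every ρ tested, when gestation was the sole driver. With a separate severity factor (loadings 0.4 to 0.5, correlated 0.3 to 0.7 with gestation), two classes were still chosen in 100%. With two real classes 0.6 SD apart and membership strongly tied to gestation, detection fell from 100% to 20% and 0% in the two settings run.

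**The case against.** The strongest reply is that the protocol fixes no such rule. It names latent class analysis, and section 11.2 defers methods to a separate SAP, which was not available here. Local independence, BIC and unconditioned indicators are assumptions of this check. With a common full within-class covariance, two classes were chosen in 0% of gradient datasets at 0.3 to 0.5 (20 replicates). This stands: the figures describe standard practice, not a fixed plan, and the absence of a class-number rule is no fault of the protocol. It does not answer the wording of the outcome. Allowing one class under BIC was already part of the simulations and did not prevent the splitting.

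Other text also bears on the point. Section 2.1 intends to delineate gestation's influence on markers. Section 11.2 lists continuous methods such as principal components. Objective 12 examines pathways linked to the endotypes. Section 11.1 foresees clinical covariates in the BPD model. These reduce the harm, but none makes the endotype claim depend on classes fitting better than a continuum. The trajectory step does not do so either: it is itself a finite mixture, and without an outside cohort it is not external validation.

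Gestation might be read into antenatal factors. A variable the protocol calls a major determinant should nevertheless be named.

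A reader might also infer that the class model must be conditioned on gestation. The documents do not support this. Section 2.1 ties lung injury to developmental stage, so gestation may be part of an endotype, and removing it can hide real classes.

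**Conclusion.** The concern holds in a limited form. The primary outcome, as worded, can be met when only a smooth gradient exists, and no stated result counts against it. Under locally independent models with BIC, this becomes the usual result once most indicators correlate about 0.3 to 0.4 or more with gestation or severity. At 0.2 or less, one class is usually returned.

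A reader might infer that endotypes would be found almost regardless of the truth. That does not follow: the protocol gives no correlations, weak gradients do not produce the effect, and a model allowing within-class covariance avoids it. The sizes rest on a linear gradient, normal noise and equal correlations across indicators, which is favourable to the effect for mixed clinical, protein and imaging data.

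The point is worth correcting before analysis, but it does not invalidate the study.

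**What to change.** Amend the synopsis and Table 3a, and carry the same wording into the SAP:

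1. State that a one-class or continuum result is possible and would be reported as the primary finding.
2. Compare the chosen class model with a continuous one-factor (or factor-mixture) model on the same indicators. Describe the result as distinct endotypes only if the class model fits better; otherwise report a severity continuum.
3. Name gestational age and sex in the confounder lists, and report a gestation-conditioned class model as a sensitivity analysis, not as the mandatory primary model.
4. Stop describing the trajectory step as external validation unless an outside cohort is named.

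The cost is wording and a few extra model fits on data already planned. Discrimination is imperfect: in the simulations the factor model identified the gradient in about 67% to 100% of datasets at correlations 0.3 to 0.5. The study may also have to report a continuum.

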4.3 Study population

4.3.1 Eligibility Criteria

Infants born between 22+0 and 31+6 weeks' gestation admitted to a participating centre who meet all the inclusion criteria and none of the exclusion criteria are eligible for enrolment on the BLUEPRINT study.

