4.3.3 Exclusion Criteria

If any of the following exclusion criteria are met, the infant will be ineligible for enrolment on this study:

1. Infants with a known major congenital anomaly (such as oesophageal atresia and central nervous system anomalies), congenital cardiac disease, congenital diaphragmatic hernia, congenital lung abnormalities and/or pulmonary hypoplasia.
2. Pulmonary hypoplasia due to anhydramnios **or** oligohydramnios before 22 weeks in which the neonatal clinician anticipates that pulmonary hypoplasia related respiratory failure will be the major respiratory problem in early postnatal life.
3. Primary cause of admission unrelated to prematurity.
4. Refusal of informed consent by their legally acceptable representative.
5. The infant does not have a parent/legal representative who can provide informed consent or consent cannot be obtained before 72 hours of age.

In addition, any infant identified by the treating medical team may be excluded from the study at the request of the treating clinician in consultation with the site lead investigator.

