6.2.4.5 Infant handling and safety during LUS and EIT

There will be no excessive handling associated with the ultrasounds or EIT required for this study. Infants will only be repositioned for image acquisition if it is deemed appropriate by the treating clinician and the bedside nurse midwife. If the infant is deemed clinically unstable for data acquisition, the procedure will be deferred. The site investigators will work closely with the treating clinician and bedside nurse/midwife to ensure the safe acquisition of ultrasound and images. Disruption to routine care will be minimised by coordinating data acquisition with clinical care.

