6.2.5 Blood Sampling and plasma isolation

Details of blood sampling and processing methodology are outlined in the BLUEPRINT Lab Processing Manual.

A minimum sample volume of 0.2ml of whole blood is required at each timepoint to perform the mass spectrometry analysis. Whole blood samples (0.5ml) will be collected into EDTA microtubes by a research or bedside nurse via either umbilical arterial line or capillary access. The required 0.2 - 0.5 ml of whole blood is consistent with the volume of blood required for common clinical investigations in preterm infants (approximately 0.3-0.5 mL for electrolyte or full blood count analysis) and represents between 0.17-0.5% of circulating blood volume (500-1500 g weight).

Blood samples will be collected at 72 hours (± 12 hours) and Day 7 (± 12 hours) post-birth from all enrolled infants. Where possible, arterial sampling will be used as this is less invasive for the infant. Capillary sampling involves breaching the skin (heel) using a micro-lancet. Micro-lancet capillary sampling is common practice in all Victorian NICUs and considered standard of care when arterial access is not available. Both arterial and capillary sampling will be conducted in accordance with current NICU blood sampling guidelines at participating sites. The ± 12 hours sampling window allows for the impact of blood sampling on the infant to be limited. Capillary blood samples will be matched to routine clinical sampling timelines to ensure there are no additional skin breaches associated with participation in the project. If routine sampling is not occurring within the allowable ± 12 -hour window, a protocol deviation will be noted in the RedCap database. All blood samples will be performed by the bedside nurse/midwife, phlebotomist or doctor who will be instructed not to persist with sampling if the procedure would expose the infant to longer distress or pain. To further ensure infant safety, a member of the study team will confirm with the clinical team the suitability of sample collection prior to each

collection based on the individual characteristics of the infant. A sample will only be taken if the treating clinician is satisfied the infant would not be harmed.

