7 POTENTIAL RISKS RELATED TO STUDY CONDUCT

7.1 Risks to the safety and rights of the study participants

Safety and adverse events will be monitored during the study to ensure timely detection of events that may affect safety or continued participation.

Blood sampling is a common practice in the NICU and low risk. There will be no additional risk related to blood sampling than those associated with routine practice with this procedure. These include the potential risk of infection from capillary and arterial sampling, and pain or discomfort from the use of a

microlancet during capillary sampling. Standard site practices will be followed for all blood sampling and research sampling will be aligned with clinical sampling to minimise the risk exposure. The BLUEPRINT protocol has been designed to utilise proteomic analysis which allows us to yield maximum amount of data from small amounts of blood. The volume of blood required for this research study is very small (0.5ml per sample, two samples per patient) and adds very little to the volume of blood taken from preterm infants as part of their routine care. Many preterm infants may require a blood transfusion during their NICU care, the small volume of blood required for this study is unlikely to contribute any additional risk that the participant will require a blood transfusion or not.

There will be minimal to no excessive handling associated with the LUS and EIT recordings required for this study. Infants will only be repositioned for image acquisition if it is deemed appropriate by the treating clinician and the bedside nurse. The investigators will work closely with the treating clinician and bedside nurse to ensure the safe acquisition of LUS and EIT images. If the infant is deemed too unstable then the infant will not be studied.

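### The synopsis makes unsuitability for a scan or blood sample a mandatory ground of ineligibility; Section 4.3 has no such criterion, and Section 6 treats it as a deferred or missing measurement.

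*Protocol*

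**What the plan says.** **Synopsis, Study population.** After the gestational-age and consent conditions, the text states that "if lung imaging or blood sampling would compromise clinical care or well-being, the infant will be considered ineligible for participation in this study". The wording is mandatory. It gives no time at which tolerance is judged and does not say whether one unsuitable procedure is enough.

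**Section 4.3.** Section 4.3.1 says that infants "who meet all the inclusion criteria and none of the exclusion criteria are eligible for enrolment on the BLUEPRINT study". Section 4.3.3 opens with "If any of the following exclusion criteria are met, the infant will be ineligible for enrolment on this study" and numbers five grounds: major anomaly, pulmonary hypoplasia, admission unrelated to prematurity, refusal, and no valid consent by 72 hours. None concerns imaging or sampling. A discretionary sentence follows the list: "any infant identified by the treating medical team may be excluded from the study at the request of the treating clinician", after consulting the site lead. No ground for the request is specified.

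**Section 6.** In 6.2.4.1, EIT recordings are skipped when readjusting the belt would disturb care. In 6.2.4.2 the ultrasound team comes back later. In 6.2.4.5, "If the infant is deemed clinically unstable for data acquisition, the procedure will be deferred". In 6.2.5, "A sample will only be taken if the treating clinician is satisfied the infant would not be harmed". These provisions act on one measurement and say nothing about eligibility.

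**Section 7.1.** "If the infant is deemed too unstable then the infant will not be studied". This can mean one missed assessment or removal from the study.

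**Section 11.3.** Incomplete imaging and plasma sets are expected and are to be handled as missing data.

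**The concern.** The primary objective is to define respiratory phenotypes and endotypes from the first 7 days of life in infants of 22+0 to 31+6 weeks. Consent may be obtained up to 72 hours after birth, so some infants reach the eligibility decision while they are unstable. That instability belongs to the phenotype under study. A rule that makes it an entry failure selects the cohort on a variable related to what the study sets out to describe.

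An infant refused at entry contributes nothing. Yet the antenatal and NICU clinical data (6.2.3), BPD status at 36 weeks (6.2.7) and the questionnaire follow-up at 1 and 2 years (6.2.9) need neither an early scan nor a plasma sample. An infant who is enrolled but misses a scan still supplies all of these, and the gap can be handled at analysis. Infants lost at entry cannot be recovered.

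Because two rules are in print, sites could also differ in which one they apply, and selection would then be mixed up with site.

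**Working it through.** The plan gives no figure on this point, so the check is mainly a comparison of texts.

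**Step 1: the same situation under each provision.** Take an infant for whom a scan or sample would be unsuitable.

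| Place | Level at which it acts | Consequence |
|---|---|---|
| Synopsis, Study population | infant | ineligible, mandatory |
| 4.3.1 with 4.3.3, items 1–5 | infant | no such criterion; eligible |
| 4.3.3, closing sentence | infant | exclusion possible on request; no ground specified |
| 6.2.4.1, 6.2.4.2, 6.2.4.5 | one imaging assessment | omitted or deferred |
| 6.2.5 | one blood sample | not taken |
| 7.1 | unclear | assessment or infant |
| 11.3 | data set | missing data |

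The synopsis is the only provision that makes the situation a compulsory bar to entry. The provisions in Section 6 and the expectation in 11.3 make sense only if such infants can be in the study.

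**Step 2: who is exposed.** Under 4.4.2 consent may be antenatal, and the infant is enrolled if still eligible at birth. An infant already enrolled who becomes unstable near 72 hours has passed the eligibility check. Section 6.3.1 permits permanent discontinuation for conditions in the exclusion list, and unsuitability for a procedure is not on that list. The clear conflict therefore concerns infants not yet enrolled when they are judged unsuitable.

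**Step 3: a concrete consequence.** Section 12.3 lists enrolment of an ineligible infant as a protocol deviation. Enrolling the infant in Step 2 is a deviation under the synopsis and correct under 4.3.

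**Step 4: does it affect sample size?** Section 11.1 gives minimum sizes of 500, 550 and 600 for 10, 11 and 12 predictors, with BPD prevalence 0.69 and C-index 0.75. Recoding the binary-outcome criteria (shrinkage 0.9, simulated Cox–Snell R² 0.162) gives 504, 555 and 605, within 3% of the stated values. As an illustration only, suppose a share f of infants is removed and all of them would have had BPD. This is an extreme assumption, and f is not in the documents. Prevalence among those left is (0.69 − f)/(1 − f):

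- f = 2%: 0.67/0.98 = 0.684; minimum for 11 predictors 548
- f = 5%: 0.64/0.95 = 0.674; minimum 540
- f = 10%: 0.59/0.90 = 0.656; minimum 525
- f = 20%: 0.49/0.80 = 0.6125; minimum 502

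The required number falls rather than rises. The issue is who enters the cohort, not how many.

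**The case against.** **The body has its own routes out.** Section 4.3.3 allows exclusion at the clinician's request, 6.1 has suitability re-confirmed before the 72-hour and Day 7 procedures, 6.3.1 allows discontinuation in the infant's best interest, and 7.1 may mean removal. This stands: the synopsis is not the only possible source of selection, and it would be wrong to say that the body only ever defers. A discretion is still not a mandatory bar, and the ambiguity in 7.1 adds to the inconsistency.

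**Sites screen from the numbered list.** Sections 6.2.1 and 6.2.3 record eligibility as meeting all inclusion and no exclusion criteria. This makes use of the synopsis rule less likely. It does not remove a rule stated in mandatory terms in the same protocol.

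**The gain for the primary analysis is unknown.** Endotypes combine clinical, plasma and imaging measures, and Section 11.3 leaves the minimum data set to the SAP. Infants without a scan or sample might not enter that analysis. This stands for the endotype analysis, but their clinical, BPD and follow-up data would still be kept.

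**A stronger reading to avoid.** A reader might infer that the sickest infants are being removed, and might size this by applying an assumed share to the roughly 2250 eligible births in Section 11.1 and linking it to the 7% mortality. The documents do not support that. They give no share, and only 20–25% of those births are to be recruited. The 7% is all-cause mortality, whereas Section 6.2.7 codes as severe BPD only respiratory deaths between 14 days and 36 weeks' PMA.

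**Conclusion.** The contradiction holds on the text. The synopsis imposes a mandatory ground of ineligibility that Section 4.3 does not contain and that Section 6 and Section 11.3 handle as a deferred, omitted or missing measurement. It clearly affects infants not yet enrolled when they are judged unsuitable for a procedure.

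Selection against unstable infants is a conditional inference: it follows if sites apply the synopsis and if the infants concerned differ in respiratory course from those enrolled. Its size cannot be estimated from the documents, and the prevalence figures above only illustrate an extreme assumption. The sample-size calculation is unaffected. Because entry losses cannot be repaired at analysis and the correction is cheap, the text should be reconciled before it shapes recruitment.

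**What to change.** Reconcile the synopsis, Section 4.3.3 and Section 7.1 so that one entry rule applies. For cohort definition, the reading consistent with Section 6 and Section 11.3 is that unsuitability for a given scan or sample affects that measurement only, with clinical, BPD and follow-up data still collected. The clinical team's veto over each procedure would stay exactly as it is.

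Keep the clinician-requested exclusion if it is wanted, but record its ground in the REDCap screening log, with gestational age and respiratory support, so that selection can be described. Section 6.2.1 already has the log show eligibility status, and Section 8.2.3 already requires reasons for non-participation. What is added is the specific ground and the two descriptors.

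The cost is a wording amendment and two or three log fields. The small downside is that more enrolled infants may have a missing early scan or sample, which the missing-data rules would need to cover.
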